7.1.1. Liver Chemistry Stopping Criteria

Liver chemistry stopping, and increased monitoring criteria have been designed to assure participant safety and evaluate liver event etiology.

Discontinuation of study intervention for abnormal liver tests should be considered by the Investigator when a participant meets one of the conditions outlined in the algorithm or if the Investigator believes that it is in the best interest of the participant.

- Liver Safety Algorithms and Required Actions and Follow up Assessments can be found in [Appendix 3](#).

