10.3. Appendix 3: Liver Safety: Required Actions and Follow-up Assessments

Phase III-IV liver chemistry stopping and increased monitoring criteria have been designed to assure participant safety and evaluate liver event aetiology (in alignment with the FDA premarketing clinical liver safety guidance).

<http://www.fda.gov/downloads/Drugs/GuidanceComplianceRegulatoryInformation/Guidances/UCM174090.pdf>

Table 7 Phase III-IV liver chemistry stopping criteria and required follow up assessments

Liver Chemistry Stopping Criteria - Liver Stopping Event	
Alanine Transaminase (ALT)-absolute	ALT \geq 8x ULN
ALT Increase	ALT \geq 5x ULN but $<$ 8x ULN persists for \geq 2 weeks ALT \geq 3x ULN but $<$ 5x ULN persists for \geq 4 weeks
Bilirubin^{1, 2}	ALT \geq 3x ULN and bilirubin \geq 2x ULN ($>$ 35 % direct bilirubin)
International Normalized Ratio (INR)²	ALT \geq 3x ULN and INR $>$ 1.5, if INR measured
Cannot Monitor	ALT \geq 5x ULN but $<$ 8x ULN and cannot be monitored weekly for \geq 2 weeks ALT \geq 3x ULN but $<$ 5x ULN and cannot be monitored weekly for \geq 4 weeks
Symptomatic³	ALT \geq 3x ULN associated with symptoms (new or worsening) believed to be related to liver injury or hypersensitivity
Required Actions and Follow up Assessments following ANY Liver Stopping Event	
Actions	

 • Immediately discontinue study treatment • Report the event to GSK within 24 hours of occurrence of the SAE per process provided in the Study Reference Manual (SRM) 	

 • Viral hepatitis serology⁴ • Only in those with underlying chronic hepatitis B at study entry (identified by positive hepatitis B surface antigen) quantitative hepatitis B DNA and hepatitis delta antibody⁵. 	

Liver Chemistry Stopping Criteria - Liver Stopping Event	

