
Liver Chemistry Stopping Criteria - Liver Stopping Event	

 Monitor participants weekly until liver chemistries resolve, stabilize or return to within baseline 	

 1. Serum bilirubin fractionation should be performed if testing is available. If serum bilirubin fractionation is not immediately available, discontinue study treatment for that participant if $ALT \geq 3x ULN$ and bilirubin $\geq 2x ULN$. Additionally, if serum bilirubin fractionation testing is unavailable, record presence of detectable urinary bilirubin on dipstick, indicating direct bilirubin elevations and suggesting liver injury. 2. All events of $ALT \geq 3x ULN$ and bilirubin $\geq 2x ULN$ ($>35\%$ direct bilirubin) or $ALT \geq 3x ULN$ and $INR > 1.5$, if INR measured which may indicate severe liver injury (possible 'Hy's Law'), must be reported as an SAE (excluding studies of hepatic impairment or cirrhosis); INR measurement is not required and the threshold value stated will not apply to participants receiving anticoagulants 3. New or worsening symptoms believed to be related to liver injury (such as fatigue, nausea, vomiting, right upper quadrant pain or tenderness, or jaundice) or believed to be related to hypersensitivity (such as fever, rash or eosinophilia) 4. Includes: Hepatitis A IgM antibody; Hepatitis B surface antigen and Hepatitis B Core Antibody (IgM); Hepatitis C RNA; Cytomegalovirus IgM antibody; Epstein-Barr viral capsid antigen IgM antibody (or if unavailable, obtain heterophile antibody or monospot testing); Hepatitis E IgM antibody 5. If hepatitis delta antibody assay cannot be performed, it can be replaced with a PCR of hepatitis D RNA virus (where needed) [Le Gal, 2005]. 6. PK sample may not be required for participants known to be receiving placebo or non-GSK comparator treatments. Record the date/time of the PK blood sample draw and the date/time of the last dose of study treatment prior to blood sample draw on the eCRF. If the date or time of the last dose is unclear, provide the participant's best approximation. If the date/time of the last dose cannot be approximated OR a PK sample cannot be collected in the time period indicated above, do not obtain a PK sample. Instructions for sample handling and shipping are in the SPM. 	

Table 8 Phase III-IV liver chemistry increased monitoring criteria with continued therapy

Liver Chemistry Increased Monitoring Criteria – Liver Monitoring Event	

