Criteria	Actions

$ALT \geq 5x ULN$ and $<8x ULN$ and bilirubin $<2x ULN$ without symptoms believed to be related to liver injury or hypersensitivity, and who can be monitored weekly for 2 weeks.
 
OR
 
$ALT \geq 3x ULN$ and $<5x ULN$ and bilirubin $<2x ULN$ without symptoms believed to be related to liver injury or hypersensitivity,
	
 Notify the GSK medical monitor within 24 hours of learning of the abnormality to discuss participant safety. Participant can continue study treatment Participant must return weekly for repeat liver chemistries (ALT, AST, alkaline phosphatase, bilirubin) until they resolve, stabilise or return to within baseline If at any time participant meets the liver chemistry stopping criteria, proceed as described above

Liver Chemistry Increased Monitoring Criteria – Liver Monitoring Event	
and who can be monitored weekly for 4 weeks.	
• If ALT decreases from ALT ≥ 5x ULN and < 8x ULN to ≥ 3x ULN but < 5x ULN, continue to monitor liver chemistries weekly.• If, after 4 weeks of monitoring, ALT < 3x ULN and bilirubin < 2x ULN, monitor participants twice monthly until liver chemistries normalize or return to within baseline.

References

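### Protocol Section 7.1.1 makes stopping for any liver-algorithm condition discretionary, which contradicts the mandatory stop for liver stopping events in Appendix 3, Table 7

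*Protocol*

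**What the plan says.** Protocol Section 7.1.1 opens by naming both kinds of criteria: "Liver chemistry stopping, and increased monitoring criteria have been designed to assure participant safety and evaluate liver event etiology". It then gives one instruction on treatment. "Discontinuation of study intervention for abnormal liver tests should be considered by the Investigator when a participant meets one of the conditions" in the algorithm, or when the investigator judges that stopping is best for the participant. Its only bullet is a pointer: "Liver Safety Algorithms and Required Actions and Follow up Assessments can be found in" Appendix 3.

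Appendix 3 (Section 10.3) treats the two kinds of event differently.

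- **Table 7, stopping events.** The criteria are followed by the heading "Required Actions and Follow up Assessments following ANY Liver Stopping Event", and the first action is "Immediately discontinue study treatment". The same table bars restarting treatment unless the protocol allows it, and requires permanent discontinuation where restart is not allowed. Footnote 1 adds a direct order for the bilirubin criterion: "If serum bilirubin fractionation is not immediately available, discontinue study treatment for that participant if" ALT is at least 3x ULN and bilirubin at least 2x ULN.
- **Table 8, increased monitoring events.** Treatment can continue with weekly liver chemistries. A participant who later meets a stopping criterion is sent back to the Table 7 actions.

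**The concern.** One discretionary phrase is attached to every condition in the algorithm. It suits the monitoring events and the investigator's own judgement. It does not suit the stopping events, for which Appendix 3 leaves no choice. Section 7.1.1 does not separate the two groups and does not say that the appendix prevails.

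The neighbouring rules make the contrast easy to notice. The QTc, pregnancy and COVID-19 rules in Sections 7.1.2 to 7.1.4 are all written as mandatory, so a reader could take the softer liver wording as deliberate.

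What is at stake is participant safety and uniform conduct across sites. The Table 7 events include possible Hy's Law cases, which Appendix 3 and Section 10.6.2 require to be reported as SAEs. With two wordings in force, a site and a monitor could also disagree on whether continued dosing after a Table 7 event is a protocol deviation, in a study whose Section 8 bars waivers.

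**Working it through.** No figure in the plan is in question, so the check is a comparison of texts and a count of table rows.

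**Conditions covered by the Section 7.1.1 sentence**

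- Table 7: ALT at least 8x ULN (1), persistent ALT increase (2), bilirubin (1), INR (1), cannot monitor (2), symptomatic (1). Total 1 + 2 + 1 + 1 + 2 + 1 = 8.
- Table 8: ALT 5x to below 8x ULN (1), ALT 3x to below 5x ULN (1). Total 1 + 1 = 2.
- All conditions: 8 + 2 = 10.

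This counts rows. It does not measure how often any of them would occur.

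**What each text requires**

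| Situation | Section 7.1.1 | Appendix 3 | Compatible? |
|---|---|---|---|
| ALT at least 8x ULN | Consider stopping | Table 7: stop at once | No |
| ALT at least 3x ULN, bilirubin at least 2x ULN, fractionation not immediately available | Consider stopping | Table 7, footnote 1: stop | No |
| ALT 5x to below 8x ULN, weekly monitoring not possible | Consider stopping | Table 7: stop at once | No |
| ALT 5x to below 8x ULN, bilirubin below 2x ULN, no symptoms, weekly monitoring possible | Consider stopping | Table 8: may continue | Yes |
| Other liver abnormality, investigator thinks stopping is best | Consider stopping | No rule | Yes |

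The other Table 7 rows behave like the first line, because the required action follows any stopping event. The conflict therefore covers the 8 Table 7 conditions. There is none for the 2 Table 8 conditions: an investigator may consider stopping and still be allowed to continue.

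**How firmly Appendix 3 states the stop.** It does so in the first Table 7 action, in the restart and permanent-discontinuation lines, and in footnote 1. The Table 8 line on later meeting a stopping criterion is a cross-reference to those actions and does not state the stop itself.

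**How many participants could be affected.** The Schedule of Activities (Section 1.3) has 0 scheduled liver chemistry tests, so the algorithm applies only when liver tests are done for another reason. Exclusion criterion 13 removes unstable liver disease. The documents give no liver event rate, so no expected number can be calculated.

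**The case against.** The strongest reply is that Section 7.1.1 cannot be applied alone. It contains no ALT multiple and no bilirubin, INR or symptom rule. To know that a condition is met, a site must open Appendix 3, where the criteria are followed directly by the required stop. On this view Section 7.1.1 is an umbrella sentence over stopping events, monitoring events and investigator-initiated stops, and the specific text governs the general. Other safeguards exist: Table 7 calls for reporting to the sponsor within 24 hours, Table 8 for notifying the medical monitor within 24 hours, and Section 8 for immediate discussion of safety concerns with the sponsor. Section 8.2.8 also restates the COVID-19 stop in softer terms than Section 7.1.4, which points to uneven drafting and not to a deliberate choice.

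Most of this stands, and it sets the limits of the point. Two stronger readings that a reader might infer are not supported:

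- *That a site following Section 7.1.1 alone would keep dosing after a stopping event.* The section gives too little to reach any such decision, and the place it sends the reader orders the stop.
- *That the ALT bands shared by Tables 7 and 8 leave sites unsure which table applies.* The tables separate them. Table 7 takes the participant who meets the ALT band "and cannot be monitored weekly for" the stated period. For the 5x to below 8x band, Table 8 takes the participant with bilirubin below 2x ULN, no symptoms "and who can be monitored weekly for 2 weeks".

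The reply does not remove the contradiction. Section 7.1.1 refers to required actions but states no precedence, and its sentence says in terms that discontinuation is for the investigator to consider when a condition is met. A reader who has both texts open still has two answers for a Table 7 event.

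**Conclusion.** The point holds as an internal contradiction in an operative safety rule. For all 8 Table 7 conditions, Section 7.1.1 offers discretion where Appendix 3 requires an immediate stop.

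The practical risk is low. It is that a site or monitor reads Section 7.1.1 as giving the investigator discretion over the required stop, for the few participants who have unscheduled liver tests. That they will be few is an inference from the absence of scheduled liver chemistry and from the exclusion of unstable liver disease; it is not a calculated rate.

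A reader might also infer some consequence for the analysis, because treatment discontinuation is the intercurrent event in the primary and secondary estimands. The documents do not support that. The estimands treat discontinuation in the same way whether or not a liver event caused it, and no endpoint definition or sample size figure depends on the liver rule. The case for changing the text rests on participant safety and consistent conduct.

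**What to change.** Replace the discretionary sentence in Section 7.1.1 with:

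*Study intervention must be discontinued immediately when any Table 7 liver stopping criterion is met; for Table 8 monitoring events treatment may continue with the required monitoring, and the Investigator may also stop treatment at any time if this is in the participant's best interest.*

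The cost is one sentence in a protocol amendment. Appendix 3 stays as it is, and no test, visit or data item is added.

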7.1.2. QTc Stopping Criteria

Details on performing ECG assessments can be found in Section [8.2.6](#).

- The *same* QT correction formula *must* be used for *each individual participant* to determine eligibility for and discontinuation from the study. This formula may not be changed or substituted once the participant has been enrolled. Safety ECGs and other non-protocol specified ECGs are an exception.
- For example, if a participant is eligible for the protocol based on QT interval corrected for heart rate by Bazett's formula (QTcB), then QTcB must be used for discontinuation of this individual participant as well.
- Once the QT correction formula has been chosen for a participant's eligibility, the *same formula* must continue to be used for that participant *for all QTc data being collected for data analysis*.
- The QTc should be based on averaged QTc values of triplicate electrocardiograms obtained over a brief (*e.g.*, 5-10 minute) recording period.
- For this study, the following QTc stopping criteria will apply and lead to withdrawal from study treatment:
 - an increase in QTc by > 60 msec from baseline
 - or development of a QTc > 530 msec (based on an average of triplicate ECGs)
 - NOTE: These criteria should be based on the average QTc value of triplicate ECGs. For example, if an ECG demonstrates a prolonged QT interval, two more ECGs will be obtained over a brief period and then the averaged QTc value of the three ECGs will be used to determine whether the participant should be discontinued from the study.

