3. OBJECTIVES AND ENDPOINTS/ESTIMANDS

Objectives	Estimands/Endpoints
Primary	

 • To evaluate the safety profile of FF/UMEC/VI over 12 weeks in patients from India 	
The primary Estimand is defined by the following:
 
 • Endpoint: incidence of adverse events (AE), serious adverse events (SAE) and adverse events of special interest (AESIs). • Summary number and percentage of participants experiencing an AEs, SAEs and number and percentage of participants experiencing AESIs by system organ class and by preferred term. • Population of interest: COPD patients in India. • Key intercurrent events: discontinuation of treatment • Strategy for intercurrent events: a While on Treatment strategy will be used for treatment discontinuation. This estimates the percentage of participants experiencing an AE or SAE while taking treatment. • Participants that test positive for COVID-19 will immediately discontinue study treatment. Therefore COVID-19 will be included as the intercurrent event of study treatment discontinuation and will be handled with While on Treatment strategy for the primary estimand 
A supplementary estimand will be defined using identical properties as for the primary estimand (summary measure, population of interest and key intercurrent events), however this supplementary

Objectives	Estimands/Endpoints
	
estimand will report all AEs regardless of the discontinuation of study treatment.
 
Endpoints:
 
 • Incidence of AEs, SAEs and AESIs 
Strategy for intercurrent events:
 
 • Treatment policy strategy will be used for treatment discontinuation. This summary will therefore be inclusive of all on-treatment and post-treatment AEs.
Secondary	

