7. DISCONTINUATION OF FF/UMEC/VI AND PARTICIPANT DISCONTINUATION/WITHDRAWAL

7.1. Discontinuation of FF/UMEC/VI

Participants have the right to discontinue FF/UMEC/VI before the end of the study. A participant may also be asked to discontinue FF/UMEC/VI at the Investigator's discretion.

Participants that permanently stop FF/UMEC/VI should return to the clinic as soon as possible, in order to complete the Treatment Discontinuation visit. The evaluations and procedures to be completed are outlined in the SoA (Section 1.3)

Participants that discontinue FF/UMEC/VI are encouraged to remain in the study and every effort should be made by the Investigator/staff to keep the participant in the study, to collect important efficacy and safety data.

If possible, participants should return to the clinic to complete all scheduled visits. If this isn't possible, visits should be completed by telephone. Ideally, participants should return to the clinic to complete Visit 5, to collect important spirometry data, however, if this isn't possible, this visit could be completed by telephone. A safety follow-up phone call (Visit 6) should also be conducted 7 days after Visit 5.

Following discontinuation of study intervention, if participants are unwilling to return to the clinic for their scheduled visits, the Investigator/site staff should contact the participant by telephone at the protocol designated visit time intervals to collect the following:

- SAEs
- AEs assessed as related to study participation
- AEs resulting in discontinuation of study intervention or withdrawal from the study
- COPD exacerbations
- Concomitant medication
- A safety follow-up phone call (Visit 6) should also be conducted 7 days after Visit 5.

A participant may be withdrawn from study intervention at any time. A reason for premature discontinuation of study intervention (e.g., AE, lack of efficacy, protocol deviation, Investigator discretion, consent withdrawn etc.) must be captured in the eCRF.

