7.2. Participant Withdrawal from the Study

- A participant may withdraw from the study at any time at his/her own request or may be withdrawn at any time at the discretion of the investigator for safety, behavioural, or compliance reasons. This is expected to be uncommon.
- The participant will be permanently discontinued both from the study intervention and from the study at that time.
- If the participant withdraws consent for disclosure of future information, the sponsor may retain and continue to use any data collected before such a withdrawal of consent.
- If a participant withdraws from the study, he/she may request destruction of any samples taken and not tested, and the investigator must document this in the site study records.

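### Section 7.1.2 gives two consequences for the same QTc criteria, stopping study treatment and leaving the study, so follow-up after a QTc event is unclear (minor)

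*Protocol*

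**What the plan says.** Protocol Section 7.1.2 sets the QTc criteria and states that "the following QTc stopping criteria will apply and lead to withdrawal from study treatment". The NOTE below them, which explains how triplicate ECGs are averaged, says that the averaged value decides "whether the participant should be discontinued from the study".

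Elsewhere the two outcomes are kept apart. Section 7.1 says: "Participants that discontinue FF/UMEC/VI are encouraged to remain in the study". The synopsis likewise says that a permanent stop of study treatment does not oblige anyone to leave the study. Section 7.2, on withdrawal from the study, says: "The participant will be permanently discontinued both from the study intervention and from the study at that time". SAP Section 9.1 tabulates treatment discontinuation and study withdrawal as separate counts, each with its own reasons.

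Adverse events are collected from Visit 2 to Visit 6 (Protocol Section 8.3.1). The same section lifts the duty to look actively for events once participation has ended. The supplementary safety estimand follows a treatment-policy strategy: "This summary will therefore be inclusive of all on-treatment and post-treatment AEs". SAP Sections 17.1.2 and 18.1 add that this strategy depends on data gathered after treatment stops, and that a participant who also leaves the study becomes a missing-data problem.

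**The concern.** One section gives one trigger two outcomes, and the outcomes differ in what data are gathered afterwards. Two sites with the same QTc finding could act differently, both with protocol text behind them. One would record a treatment stop and continue to Visit 6. The other would record a study withdrawal and end active questioning.

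The participant concerned has just had a cardiac safety finding in a study whose primary objective is safety. Section 2.3.1 names serious cardiovascular events as a risk and cites Section 7.1.2 as one of the mitigations, and cardiac arrhythmia is a subgroup of the adverse events of special interest (Table 4). What is at stake is new adverse events between the stop and Visit 6, the Visit 5 spirometry, and consistent classification in the disposition table.

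**Working it through.** The point contests no figure in the plan, so the check is mainly a comparison of text.

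1. **Same criteria?** Yes. The NOTE explains how the QTc value for the stopping criteria directly above it is obtained. It sets up no separate rule.

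2. **Are the two outcomes synonyms in this protocol?** No. Section 7.1 and the synopsis describe participants who stop treatment and stay. Section 7.2 describes leaving the study, which ends both. SAP Section 9.1 counts them separately. Section 7.2 also allows the investigator to withdraw a participant for safety reasons, so a site could read the NOTE literally without obvious error.

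3. **What changes if a site follows the NOTE?**
   - Active questioning about new adverse events may end before Visit 6 (Section 8.3.1).
   - Visit 5 spirometry is lost. The Schedule of Activities marks no spirometry at the treatment discontinuation visit, so for a stop after Visit 3, Visit 5 is the only later reading.
   - Still in place: follow-up of events that are serious, related or the cause of discontinuation (Section 8.3); follow-up of recorded events to resolution, stabilisation or other explanation (Section 8.3.3); and notification of related SAEs the investigator learns of after discharge (Section 8.3.1).

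4. **Which analyses use the lost data?**
   - Primary safety estimand: while on treatment, so events up to the treatment stop count under either reading.
   - Main FEV1 analysis: values after treatment discontinuation are set to missing in any case (Protocol Section 9.3.1, SAP Section 18.1.2).
   - Supplementary safety estimand: uses post-treatment events, so it is exposed.
   - Supplementary FEV1 estimand: uses readings after a stop unrelated to COVID-19, so it is exposed. SAP Section 4 removes the protocol's condition that more than 5% must discontinue, so this analysis will be run regardless.
   - Disposition counts: exposed to inconsistent classification.

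5. **Size per affected participant.** Visit 6 is planned for Day 92. Days of active collection at risk = 92 − day of leaving:
   - Day 28: 92 − 28 = 64 days
   - Day 56: 92 − 56 = 36 days
   - Day 84: 92 − 84 = 8 days

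6. **Size across the study.** ECG is scheduled only at Screening, so an on-treatment trigger needs an unscheduled ECG. The documents give no rate. Assuming 0 to 2 participants of the planned 229, the share is 0% to 2/229 = 0.87%; one participant is 1/229 = 0.44%. Each could move a supplementary incidence by at most 0.44 percentage points, and only if that participant had a new, otherwise uncounted event after leaving.

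**The case against.** The strongest reply is that the general rule is already stated. Section 7.1.2 sits under Section 7.1, which asks sites to keep participants who stop treatment, and the synopsis agrees. The one sentence in 7.1.2 that assigns a consequence names study treatment, while the NOTE is an averaging instruction given by example. This stands as a limit on how often the problem would arise. It does not remove the contradiction: the NOTE applies at the point of decision, and encouragement to stay does not clearly override it.

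A reader might infer more than the documents support in four ways.

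- **That 7.1.2 conflicts with itself in a third place**, because its opening bullet speaks of using one formula "to determine eligibility for and discontinuation from the study". That bullet concerns consistent use of a QT correction formula and assigns no consequence to a QTc value.
- **That the lack of a retention sentence in 7.1.2 is itself telling**, since the pregnancy and COVID-19 sections have one. Section 7.1.1 on liver chemistry lacks one too (continuation appears only in Appendix 3), and Section 7.1 covers all its subsections.
- **That all safety information after the stop would be lost.** Sections 8.3, 8.3.1 and 8.3.3 preserve the follow-up listed above, and the treatment discontinuation visit includes an adverse event assessment. Nor does staying guarantee full collection: Section 7.1 gives a reduced list for participants who stop treatment and will not attend the clinic.
- **That 0.44% is close to the risks in Table 5, so detection is impaired.** A share of participants is not a per-participant event risk. Table 5 gives 1 − 0.99^220 = 0.8904 for at least one event at 1% risk. Removing one participant entirely gives 1 − 0.99^219 = 0.8893, about 0.1 percentage point lower. Even that overstates the loss, because the participant stays in the ITT population with all on-treatment data.

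**Conclusion.** The contradiction is real and minor. The criteria sentence and the NOTE in Section 7.1.2 give different consequences for the same finding, and the protocol and SAP treat those consequences as distinct. The possible loss is active collection of new adverse events up to Visit 6 and the Visit 5 spirometry, in the few participants who might meet the criteria on an unscheduled ECG. It reaches only the two supplementary treatment-policy estimands and the disposition counts. The primary estimand and the main FEV1 analysis are largely unaffected, and no sample-size figure changes.

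This rests on two assumptions: that some site would act on the NOTE as written, and that QTc events are rare. The second is inferred from the ECG schedule, not from any rate in the documents. The conclusion makes no judgement on the QTc thresholds or on which consequence is right.

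**What to change.** Reconcile the criteria sentence and the NOTE in Section 7.1.2 so that both state the same consequence. Add a cross-reference to the section that then governs follow-up and adverse event collection, Section 7.1 or Section 7.2 according to the sponsor's choice. For consistency of terms, align the opening bullet's phrase with that choice.

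The cost is a wording change in the protocol. No analysis, sample size or visit schedule needs to change. If the wording cannot be changed in time, a written clarification to sites and a note on how such cases are classified in the disposition table would serve the same purpose.
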